# Protocol Synopsis

Protocol Title:	DSUVIA Early Evaluation of Pain (DEEP) Trial				
Protocol Number:	STUDY21100180				
NCT Number:	NCT05288348				
Version # and Date:	Version 3 1/12/2023				
Investigational Drug:	DSUVIA as compared to standard care pain treatment				
Trial Sites:	
 
Clinical Coordinating Center
 
University of Pittsburgh, University of Pittsburgh Medical Center, Co-PI [name], Co-PI [name]
 
Additional Sites:
 
TBD
 
				
Funding Agency	Department of Defense				
Study Aims:	
 
Objectives for the study aims: 
 
(1) To conduct a prospective, randomized, interventional trial to examine effectiveness, safety, and acceptability of DSUVIA compared to standard care pain treatment in an emergency department (ED) setting in patients following traumatic injury with moderate to severe pain.
 
(2) To analyze pain treatment effectiveness outcomes including: 
 
a. Verbally administered Numeric Rating Scale (VNRS) for clinical pain measurement (0-100) 30 minutes after pain medication administration
 
b. Adverse effects and events related to pain medication(s) including nausea/vomiting, headache, dizziness, hypoxia, hypotension, and need for advanced airway
 
c. Verbally administered Numeric Rating Scale (VNRS) for clinical pain measurement (0-100) at 30-minute intervals until discharge from the ED (up to 120 minutes) or rescue narcotic administration
 
d. Patient Global Assessment (PGA) of Pain Control at 30-minute intervals until discharge from the ED (up to 120 minutes) or rescue narcotic administration
 
e. Richmond Agitation-Sedation Scale score at 30-minute intervals until discharge from the ED (up to 120 minutes) or rescue narcotic administration
 
f. Time-weighted summed pain intensity difference (SPID) at 30-minute intervals until discharge from the ED (up to 120 minutes) or rescue narcotic administration
 
 
 

				

	
 
g. Number of rescue doses of narcotic at 30 minutes and during ED stay (up to 120 minutes)
 
h. Time to reduction of NRS pain score of 10 points
 
i. Cognitive function assessment with the Six Item Screener (SIS) at 30 minutes
 
j. Healthcare Professional Global Assessment (HPGA) of the Method of Pain Control at 30 minutes
 
k. Acceptability to health care providers survey
 
			
Study Design:	Prospective, randomized, interventional trial			
Planned Sample Size:	N= 150 total; 75 each arm			
Planned Study Duration:	3 years			
Major Inclusion Criteria:	
 
Trauma activation (Level I, II or III)
 
Age 18 years to 70 inclusive.
 
Blunt or penetrating injury
 
Need for pain treatment based upon an VNRS clinical pain measurement ≥ 50
 
Estimated time in Emergency Department > 30 minutes following informed consent
 
			
Major Exclusion Criteria:	
 
Advanced airway management prior to 1st dose administration
 
Known allergy to fentanyl, sufentanil, or meperidine
 
Known prisoner
 
Known pregnancy
 
ED pain treatment contraindicated per standard care
 
Estimated BMI >40
 
Significant respiratory depression
 
Known or suspected gastrointestinal obstruction, including paralytic ileus
 
			
Primary Outcome:	Verbally administered Numeric Rating Scale (VNRS) for clinical pain measurement (0-100) at 30 minutes following randomized medication administration			

## I. Objective and Specific Aims

Our objective is to perform a prospective, randomized, interventional trial of Emergency Department (ED) administration of DSUVIA versus standard care pain management comparing pain treatment outcomes in injured patients with moderate to severe pain.

**AIM #1:** To determine if, among injured patients with moderate to severe pain, treatment with DSUVIA compared to standard care pain treatment in the ED reduces the Verbally administered Numeric Rating Scale (VNRS) for clinical pain measurement (0-100) at 30 minutes.

Hypothesis #1: Null Hypothesis: There will be no difference in the pain score at 30 minutes of patients who received DSUVIA as compared to standard care pain medicine in trauma patients

**AIM #2**: To determine if, among injured patients with moderate to severe pain, treatment with DSUVIA compared to standard care pain treatment in the ED reduces adverse effects and events related to pain medication(s) including nausea/vomiting, headache, dizziness, hypoxia, hypotension, and need for advanced airway.

Hypothesis #2: Null Hypothesis: There will be no difference in the rate of adverse events of nausea/vomiting, headache, dizziness, hypoxia, hypotension and need for advanced airway in patients who received DSUVIA as compared to standard care pain medicine in trauma patients.

**AIM #3:** To determine if, among injured patients with moderate to severe pain, treatment with DSUVIA compared to standard care pain treatment in the ED improves pain treatment effectiveness including serial VNRS scores (every 30 minutes), the need for rescue narcotic administration, the time needed to reduce the VNRS pain score by 10 points, time-weighted summed pain intensity difference, patient global assessment (PGA), Six Item Screener (SIS) cognitive assessment and Richmond Agitation-Sedation Scale scores.

Hypothesis #3: Null Hypothesis: There will be no difference in the pain treatment effectiveness, need for rescue narcotic administration, time to reduction of 10 points of VNRS pain score by 10 points, the time-weighted summed pain intensity difference, patient global assessment, Six-Item Screener and the Richmond Agitation-Sedation Scale scores in patients who received DSUVIA as compared to standard care pain medicine in trauma patients.

**AIM #4:** To determine if, among injured patients with moderate to severe pain, treatment with DSUVIA compared to standard care pain treatment in the ED improves Healthcare Professional Global Assessment (HPGA) of the Method of Pain Control and health care provider survey scores.

Hypothesis #4: Null hypothesis: There will be no difference in the Healthcare Professional Global Assessment (HGPA) of the method of pain control and healthcare provider survey scores in patients who received DSUVIA compared to standard care pain medication in trauma patients.

## II. Background and Significance

The management of pain following an acute injury is an essential part of caring for a trauma victim in both the military and civilian systems. Providing analgesia as soon as practicable is humane, reduces suffering, moderates physiologic complications of trauma, and may mitigate the incidence of long-term sequelae such as chronic pain and PTSD. Reviews of pain management demonstrate high variability and inconsistency in the reporting, assessment, and treatment of pain. Pain management is further complicated by fears and misconceptions of adverse events, chemical dependency, and implicit bias. Current prehospital pain management strategies rely on parenteral medications to provide rapid relief because oral medications are slow in onset and absorption from intramuscular injections is unpredictable. In combat, only 7% of casualties had a pain score recorded and only 15% received any analgesic. In less austere environments, providers only assess pain in 2/3 of patients. Pain following traumatic injury is common (81%), severe (73%), infrequently treated (47%), and the management inadequate (25%).

Guidelines from the National Association of EMS Physicians (NAEMSP) recommend assessing pain in all patients, using a self-reported pain score (NRS), using opioid analgesics (morphine or fentanyl), reassessing pain and adverse effects frequently, and redosing analgesia if significant pain remains. Greater granularity in pain assessment is achieved with a verbally administered NRS which has been extensively applied in ED settings during the assessment of acute pain.

The NAEMSP guidelines focus on intravenous (IV) fentanyl and morphine because of wide availability among American EMS services. Use of IV opioids is limited by the need to obtain IV access, which can be time consuming, is associated with a significant failure rate, and may lead to increased exposure in a tactical environment. The US military uses oral transmucosal fentanyl citrate (OTFC) which can be administered without IV access, but has slow absorption. Furthermore, safety data on OTFC, outside of long-term analgesia for cancer patients, is not well described. Given these significant limitations, an alternative to IV opioid analgesics in necessary. The ideal agent has robust stability, easy delivery, rapid onset, minimizes altered mental status and has a wide therapeutic index. In addition, the ideal agent would have a longer duration of action and an improved side effect profile as compared to the current standard care.

Sufentanil is a potent opioid analgesic derived from fentanyl with no active metabolites, rapid onset, and a therapeutic index superior to morphine and fentanyl. Sufentanil is highly lipophilic and rapidly achieves equilibrium in the brain; the time to analgesia is similar to IV morphine. When administered sublingually, sufentanil is 53% of the IV bioavailability within one minute and provides analgesia within 15 minutes. Sufentanil has a low incidence of side effects, with nausea, headache, dizziness, and vomiting being the most common. As with any opioid, respiratory depression and hypoxia can occur but was observed to be <1%. Similar studies found no clinically significant changes in vital signs after the administration of sublingual sufentanil in post-operative patients. Sufentanil was effective in a cohort of patients with painful injuries presenting to the ED with pain reduction seen in less than 15 minutes and persisting for 2 hours.

These data suggest that in this cohort of injured patients with moderate to severe pain, sublingual sufentanil (DSUVIA) may provide similar analgesia to IV opioids. Similar to standard care with IV fentanyl or morphine, sufentanil (DSUVIA) is effective, rapid in onset, and has a favorable side effect profile. DSUVIA has the advantage of sublingual administration, precluding the need for IV access while providing rapid analgesia. In addition, sublingual administration of sufentanil provides longer duration of analgesia compared to IV fentanyl and more rapid absorption and analgesia then OTFC. The current management of pain in this injured cohort is inadequate and demonstrates the need to determine the efficacy and safety of DSUVIA (sublingual sufentanil) as compared to standard care for pain management in the prehospital setting.

## III. Study Design/Setting

The current proposed study will be a 3-year, multi-center, open label, randomized trial utilizing 2-4 level-1 trauma centers from within the LITES network and will enroll approximately 150 patients. The University of Pittsburgh will be the Clinical Coordinating Center and the Data Coordinating Center for the study.

Study Population: Blunt or penetrating injured patients who require pain management in the Emergency Department phase of care.

#### Inclusion Criteria

- 1. Trauma activation (Level I, II or III)
- 2. Age 18-70 years inclusive.
- 3. Need for pain treatment based upon an NRS (0-100) clinical pain measurement  $\geq 50$
- 4. Estimated time in Emergency Department > 30 minutes following informed consent

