#### Exclusion Criteria

1. Advanced airway management prior to 1st dose administration

- 2. Known allergy to fentanyl, sufentanil, or meperidine
- 3. Known prisoner
- 4. Known pregnancy
- 5. ED pain treatment contraindicated
- 6. Estimated BMI >40
- 7. Significant respiratory depression
- 8. Known or suspected gastrointestinal obstruction, including paralytic ileus

Study Intervention: The study intervention will be the administration of 30 micrograms of DSUVIA in tablet form utilizing a sublingual applicator following informed consent for participation.

Study Intervention Arm: Patients randomized to the study intervention arm will receive DSUVIA via approved applicator as soon as feasible after randomization. A single dose of DSUVIA will be provided as directed on the package insert. Pre-randomization pain treatment will not be prohibited for study participation and dosage and narcotic type will be documented and recorded.

Standard Care Arm: Patients randomized to the standard care arm will receive standard care pain management. Dose administered and the respective narcotic will be recorded. Pre-randomization pain treatment will not be prohibited for study participation and dosage and narcotic type will be documented and recorded.

Randomization and Masking: Individual patients meeting all inclusion and no exclusion criteria in the emergency department will be randomized and assigned according to a 1:1 ratio of DSUVIA or standard care pain treatment using a permuted block design with variable block sizes of 4 and 6. A predefined randomization assignment will be utilized. The arm assignment will be provided in real time at the individual patient level. Trauma attending and ED physicians will not be masked to treatment assignment as the study intervention will not be blinded. Arm assignment will be concealed to all outcome assessors for follow up.

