## IV. Outcomes

**Primary Outcome:** The primary outcome for the pilot trial will be the Verbally administered Numeric Rating Scale (VNRS) for clinical pain measurement (0-100) at 30 minutes following randomized medication administration. 

Secondary Outcomes: Secondary outcomes will include adverse events including hypoxia needing supplemental oxygen (SpO2 < 90%); hypotension (systolic blood pressure < 90mmHg); advanced airway or bag mask ventilation; incidence of nausea/vomiting/headache/dizziness requiring treatment; serial (30 minute intervals until ED discharge, up to 120 minutes or rescue narcotic administration) measurements of a) VNRS for clinical pain (0-100), b) Patient Global Assessment (PGA) of Pain Control, c) Richmond Agitation-Sedation Scale (RASS) scores, and d) time-weighted Summed Pain Intensity Difference (SPID); number of rescue narcotic doses at 30 minutes and during ED stay (up to 120 minutes); time to a reduction in VNRS pain score of 10 points; patient cognitive function as assessed by the Six Item Screener (SIS) at 30 minutes; Healthcare Professional Global Assessment (HPGA) of the method of pain control at 30 minutes; and acceptability of pain treatment to health care providers.

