#### Secondary Outcome Definitions:

**Hypoxia, hypotension or need for advanced airway:** The principal safety outcome for the trial will be the incidence of serious adverse events following the first dose of analgesic following randomization including hypoxia (SpO2 < 90%), hypotension (SBP < 90 mmHg) or the need for advanced airway management (placement of an endotracheal tube, supraglottic airway or bag mask ventilation) until ED discharge (up to 120 minutes), when feasible.

Composite outcome of nausea, vomiting, headache, and/or dizziness requiring treatment: The incidence of nausea, vomiting, headache, and/or dizziness requiring treatment will be recorded for initial 30 minutes, when feasible.

Verbally administered Numeric Rating Scale (VNRS) pain measurements (0-100) at 30- minute intervals: VNRS for clinical pain (0-100) measurements at approximate 30-minute intervals until discharge from the ED (up to 120 minutes) or rescue narcotic administration, will be obtained when feasible.

**Patient Global Assessment (PGA) of Pain Control at 30-minute intervals:** The PGA of the method of pain control at approximate 30-minute intervals until discharge from the ED (up to 120 minutes) or rescue narcotic administration, will be obtained when feasible. The research team will read the following statement aloud to the subject and the response will be recorded: "Overall, would you rate this method of pain control during the last 30 minutes/hours as being poor (1), fair (2), good (3), or excellent (4)?"

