## V. Screening and Enrollment

Subjects will be identified prospectively in the ED by research personnel that are trained and familiar with the inclusion and exclusion criteria. Those patients who meet all inclusion and no exclusion criteria will be approached for informed consent, and once obtained, randomized to DSUVIA or standard care based upon the predetermined randomization assignment. Subjects will be paid \$25.00 in a Vincent Pay card upon completion of the study.

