# AIM #4: To determine if, among injured patients with moderate to severe pain, treatment with DSUVIA compared to standard care pain treatment in the ED improves Healthcare Professional Global Assessment (HPGA) of the Method of Pain Control and health care provider survey scores.

Scores to the HPGA will be based on a four-point scale. A 2x4 chi-square test will be used to compare the distribution of scores across the two treatment groups. An ordinal polytomous logistic regression model will be used to compare the distribution of proportions after controlling for stratification (sites) and baseline characteristics not balanced through random assignment. The same analysis will be repeated on the health care provider survey scores, with the modification to account for a five-level outcome.

**Sample Size**: The sample size calculations are based on the analyses of the primary aim (Aim 1) of the study. To detect a minimum effect size of 0.45, a sample size of 150 subject is needed (75 per group), assuming a type I error of 0.05, a two-sided alternative hypothesis, and 80% power. Thus, assuming a standard deviation of 21 (Karcioglu, 2003), a difference of 7.1 can be detected between the mean VNRS scores.

**Missing data**: Every attempt will be made to minimize the amount of missing data. Give the short timewindow to collect data, missing data should be minimal. However, in the event that there is missing data for the outcomes, the pattern of missingness will be evaluated. Assuming that the data will be missing at random, multiple imputation techniques will be used to impute data and carry out the proposed analyses.

**Subgroup**: Analyses will be carried out for pre-defined subgroups, specifically: sex (male/female), Injury Severity Score (ISS < or  $\ge 16$ ), age (< or  $\ge 50$ ), blunt versus penetrating injury, history of prior opioid use (Y/N), air versus ground prehospital transport, transport origin (scene versus outside ED). For all subgroup analyses, regression models will be used to assess if there is a differential treatment effect by subgroup. Regression models will include main effects for treatment and the indicator of the subgroup, as well as the two-way interaction between treatment and the subgroup indicator. A statistically significant interaction will indicate a differential treatment effect.

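### The ED-stay criterion counts 30 minutes from consent but the primary VNRS is due 30 minutes after dosing, so an eligible patient may leave the ED before the reading is due

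*Combined protocol and SAP*

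**What the plan says.** Section III, Inclusion Criteria, item 4 (repeated as item 5 in the synopsis) sets the only ED-stay requirement: "Estimated time in Emergency Department > 30 minutes following informed consent".

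Section IV times the primary VNRS "at 30 minutes following randomized medication administration". The synopsis aims use the same starting point: "30 minutes after pain medication administration".

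Section V gives the order of steps. Eligible patients "will be approached for informed consent, and once obtained, randomized to DSUVIA or standard care". Dosing follows. In Section III, patients in the intervention arm "will receive DSUVIA via approved applicator as soon as feasible after randomization". For the comparator, the text says only: "Patients randomized to the standard care arm will receive standard care pain management", with no timing.

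Under Secondary Outcome Definitions, the serial VNRS is taken at roughly 30-minute "intervals until discharge from the ED (up to 120 minutes) or rescue narcotic administration, will be obtained when feasible".

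Section VI sizes the trial as follows: "To detect a minimum effect size of 0.45, a sample size of 150 subject is needed (75 per group"), with two-sided alpha 0.05 and 80% power. It gives no rate of missing outcomes and does not inflate the sample size. Its missing-data paragraph expects little loss because the collection window is short. If outcomes are missing, it plans to look at the pattern and use multiple imputation under missing at random.

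**The concern.** The evident purpose of criterion 4 is to enrol patients who will still be available for the 30-minute reading. It counts from consent, whereas the reading counts from a later event. The protocol does tie eligibility to dosing elsewhere: the first exclusion criterion, on airway management, refers to the first dose.

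Nothing else closes the gap. No section limits the time from consent to dose, requires 30 minutes in the ED after the dose, gives a window around the 30-minute reading, or says how it is obtained once the patient has left the ED. The primary endpoint is therefore exposed in a trial with no allowance for loss. The Six Item Screener and the HPGA, also set at 30 minutes, share the exposure.

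**Working it through.** **Timing.** Let g be the minutes from consent to dosing. Because consent and randomization come before the dose, g > 0.

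- Time the criterion asks for after consent: more than 30 minutes (estimated).
- Time at which the primary reading is due after consent: 30 + g minutes.
- Patients who qualify but leave the ED first: those whose actual stay after consent is above 30 and below 30 + g minutes.

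The documents give no value for g. For assumed values of 5, 10, 15 and 20 minutes, the reading is due 35, 40, 45 and 50 minutes after consent. With g = 10, a patient who stays 35 minutes qualifies and leaves 5 minutes before the reading is due.

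**The plan's own sample size.** Inputs from Section VI: effect size 0.45, 75 per arm, two-sided alpha 0.05, 1:1 allocation.

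- Power = Φ(0.45 × √(75/2) − 1.96) = Φ(2.756 − 1.960) = Φ(0.796) = 78.7%. The t-test version gives 78.2%.
- For 80% power the normal formula needs 78 per arm (156 in total) and the t-test 79 per arm (158).

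The stated 150 is thus slightly short of 80% before any loss. That shortfall is separate from the timing point.

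**If some primary readings are missing.** The loss rates d are assumptions, because the documents supply none. Complete-case power uses n = 75 × (1 − d) per arm. The total needed to keep 75 evaluable per arm is 2 × 75/(1 − d), with each arm rounded up.

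| Assumed loss | Evaluable per arm | Power at 0.45 SD | Total N to keep 75 per arm |
|---|---|---|---|
| 0% | 75 | 78.7% | 150 |
| 2% | 73.5 | 77.9% | 154 |
| 5% | 71.25 | 76.6% | 158 |
| 10% | 67.5 | 74.4% | 168 |
| 15% | 63.75 | 71.9% | 178 |
| 20% | 60 | 69.3% | 188 |

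For example, at 10%: Φ(0.45 × √(67.5/2) − 1.96) = Φ(2.614 − 1.960) = Φ(0.654) = 74.4%.

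These figures take 0.45 as given. Section VI also states a standard deviation of 21 and a detectable difference of 7.1. Since 0.45 × 21 = 9.45, those figures do not agree with each other, but that is a different point.

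**The case against.** The best case for the plan has four parts.

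1. **Criterion 4 is an estimate made at screening.** A reader might infer that a patient expected to stay 31 minutes cannot reach the reading. The documents do not support that, since such a patient may well stay longer. What stands is that the patient may leave first. For the same reason, re-anchoring the criterion will reduce early departures, not abolish them.

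2. **Leaving the ED is not the same as losing the reading.** A reader might infer that primary outcomes are lost by design. Section IV does not confine the primary VNRS to the ED; the ED-discharge limit is attached to the serial secondary measures. Participants are trauma activations at level-1 centres, and ICU days and length of stay are among the data collected, so some will still be in the hospital. This objection stands. What remains is that no procedure says the reading is to be taken there.

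3. **The missing-data plan covers it.** It does so in part. Multiple imputation under missing at random gives a defined analysis but does not restore readings that were never taken. A patient who leaves before 30 minutes after the dose has no earlier post-dose VNRS on the serial schedule to inform the imputation, and missing at random is open to question if departure depends on pain.

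4. **Most stays may be long and delays short.** The plan schedules measurements in the ED for up to 120 minutes and asks for prompt DSUVIA dosing after randomization. Both suggest that the loss could be small. The documents cannot settle this either way.

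A reader might also infer that standard care loses more readings because IV access takes time, as Section II says it can. The standard care text names no route, and treatment before randomization is allowed, so a line may already be in place. The documents support only this much: dose timing is stated for the DSUVIA arm alone, so the delay could differ by arm.

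**Conclusion.** The mismatch is real and needs no assumption beyond dosing taking place after consent. A patient who satisfies criterion 4 may leave the ED before the primary reading is due, and the plan does not say how the reading is then obtained. The reading is at risk, not necessarily lost.

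The size is unknown. At an assumed 5% to 15% of readings missing, complete-case power at 0.45 SD falls by about 2 to 7 percentage points from 78.7%, with nothing in N = 150 to absorb it. Loss that differs by arm is a possibility and no more. This is a modest weakness that is worth correcting because it touches the primary endpoint and is cheap to remove.

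**What to change.** 1. In Section III (inclusion criterion 4) and in the matching synopsis item, count the estimated ED stay of more than 30 minutes from expected study medication administration instead of from consent.
2. In Section IV, under Primary Outcome, state that the 30-minute VNRS is taken even if the patient has left the ED for another hospital area.

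The second change protects the endpoint most directly, because the first still rests on a forecast. Patients who have left the hospital altogether would remain missing and fall under the existing missing-data plan.

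The cost is a short amendment, a few more screen failures, and staff time to follow some patients to another unit. Sample size, treatment and analysis are unchanged.
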